21 **3.7 Name:** [name]

22 **Position:** Clinical instructor

23 **Affiliation:** Division of Pediatric Critical Care Medicine, Department of Pediatrics

24 **[contact] **Mobile [contact]

25 **E-mail:** [contact]

26 **Responsibility in the project:** recruit participant, review manuscript

27

28 **4. Student support**

29 **Check ✓ in () that apply**

30 () Not associated

31 (✓) Undergrad./post grad. [name].

32 **5. Keywords:** AVCO₂, inflammatory markers, post cardiac surgery, cardiopulmonary bypass

33 **6. Background and rationale**

34 Cardiopulmonary bypass (CPB) is a potent stimulus causing systemic inflammatory response in children
35 with cardiac disease who undergone open heart surgery. Mechanisms of inflammatory generator during CPB

1 include blood contact with CPB circuit, ischemia-reperfusion injury, heparin-protamine interactions, and surgical
2 trauma. These mechanisms aggravate the activation of complement cascade, release of endotoxin, and altered
3 cytokine production which led to low cardiac output syndrome (LCOS)¹

4 The LCOS refers to declining cardiac function in the face of an elevated demand of cardiac output which
5 may lead to multiorgan failure and death. Incidence of the LCOS is approximately 25% of children after cardiac
6 surgery¹ and commonly occurs 6- 18 hours following admission to intensive care unit². Currently, there is no
7 consensus for diagnostic criteria of the LCOS and accurate detection of early cardiac output (CO) insufficiency
8 is a challenging task especially in post-operative children. Measurement CO by using thermodilution method
9 via Swan-Ganz catheterization or transesophageal echocardiography are not applicable in pediatrics setting
10 meanwhile transthoracic echocardiography immediately after post-cardiac operation is limited due to surgical
11 wound and tissue swelling. In Songklanagarind Hospital, clinicians practically use parameters such as serum
12 lactate, central venous oxygen saturations (ScvO₂), and arteriovenous oxygen difference (AVO₂) as bedside
13 surrogates of CO. However, these parameters can be influenced by multiple factors unrelated to LCOS³.
14 Hyperlactatemia in cardiac surgery could be elevated due to post-operative stress response, use of beta-
15 adrenergic agonist, hyperglycemia, or reduce lactate clearance due to transaminitis while normal values of
16 ScvO₂ can be found despite microcirculatory dysfunction and localized tissue hypoxia⁴.

17 Central venous to arterial CO₂ partial pressure difference (AVCO₂) measures the circulatory clearance of
18 tissue CO₂ and has been proven to be correlated with CO in critically ill adult patients⁵. Widening of AVCO₂
19 represents an imbalance between CO₂ clearance by CO and tissue CO₂ production. With limited data available,
20 it remains unknown whether AVCO₂ is a useful adjunctive marker for assessment CO adequacy in pediatric
21 patients after cardiac surgery with CPB.

22 Additionally, increase cytokine production both pro- (interleukin (IL)-6, IL-8, and tumor necrotic factor
23 (TNF)- α) and anti-inflammatory cytokines (IL-4, IL-10) caused by CPB-induced inflammatory activation can
24 alter multiorgan function and vascular permeability. The relationship between level of these cytokines and
25 clinical outcomes also remains uncertainty in children population.

26 We aimed to evaluate the association between AVCO₂ and inflammatory markers at 4 different time points
27 post operatively with LCOS-related poor outcome and calculate predictability of these markers to facilitate
28 earlier recognition and management LCOS in children undergone cardiac surgery with CPB.

29 30 7. Objective(s) of the study

31 **Main or Primary objective:** To compare accuracy of prediction of LCOS-related poor outcome between
32 AVCO₂ and traditional bedside surrogates (lactate, ScvO₂ and AVO₂) in children with cardiac disease who
33 undergone CPB.

[figure not shown]
34 **Secondary objectives:**

1 7.1 To evaluate association between AVCO_2 in children with cardiac disease who undergone CPB and other
 2 morbidities: 28-ventilator free day, 28-ICU free day, acute kidney injury, and deaths from any cause during
 3 hospitalization.

4 7.2 To evaluate association between level of pro- and anti-inflammatory cytokine in children who underwent
 5 CPB and LCOS-related poor outcome.

6

7 **8. Conceptual framework**

8

9 **9. Literature review**

10 AVCO_2 difference

11 A retrospective study done by Rhodes LA, et al³ evaluated correlation of AVCO_2 with other cardiac output
 12 surrogates (lactate, ScvO₂ and AVO₂) and its capacity to predict poor outcomes associated with LCOS in 139
 13 infants who underwent CPB. There were only 24.5% of poor outcome in this study. The results showed moderate
 14 correlation between AVCO_2 difference with AVO₂ ($R^2 = 0.53$; $p < 0.01$), and ScvO₂ ($R^2 = -0.43$; $p < 0.01$), but not
 15 lactate. Unadjusted ROC analysis demonstrated that AVCO_2 had lower AUC than ScvO₂, but higher AUC than
 16 serum lactate (AUC of AVCO_2 0.69 vs ScvO₂ 0.74 vs lactate 0.64). After multivariable logistic regression analysis,
 17 admission AVCO_2 remained significantly associated with poor outcome (OR, 1.3; 95% CI, 1.1-1.45), including
 18 independent association with mortality (OR, 1.2; 95% CI, 1.07-1.31). Limitation of this study include missing data
 19 of blood gas analysis and lack of simultaneous hemodynamic variables and concurrent echocardiogram. The
 20 population in this study also limited only to infant age less than 90 days. Another retrospective cohort study done
 21 in 54 Pakistan's children also showed moderate correlation between AVCO_2 and ScvO₂ ($R^2 = 0.34$), but the
 22 participants were still limited in complete repair of congenital heart defect. As accuracy of ScvO₂ depends on
 23 intracardiac structure, the correlation between AVCO_2 and ScvO₂ in incomplete repair is unknown⁶.

1 A retrospective study done by Arkamatsu T, et al⁷ evaluated the association of AVCO₂ with morbidities in 114
2 pediatrics patients who undergone CPB. The result reported poor correlation of AVCO₂ with other parameters
3 (lactate, ScvO₂). Additionally, comparing patients who had high (VACO₂ > 6 mmHg) and low gap (VACO₂ < 6
4 mmHg) of VACO₂, there was no difference of intubation time nor length of ICU stay. However, the outcome in this
5 study did not directly relate to LCOS.

6

7 There were 2 prospective and 4 retrospective studies done in adult who undergone CPB^{4, 8-12}. Some reported
8 the significant association between AVCO₂ and poor outcome^{4, 9-11} but some did not^{8, 12}. However, poor outcome
9 was defined differently in each study which might not be referred to LCOS-related complications.

10 **Inflammatory cytokines**

11 Unlike the AVCO₂ studies, most studies on inflammatory cytokine in pediatric cardiopulmonary bypass surgery
12 were prospective analysis. Allan CK, et al¹³ assessed the relationship between level of inflammatory cytokines (IL-
13 6, IL-8, IL-10, TNF α , IL-1 β , and CPR) and clinical outcome at different time points (pre CPB, post CPB at 0, 6
14 12, and 24 hours) in 93 pediatric patients. The result demonstrated that level of postoperative IL-6 and IL-8 at 0
15 and 24 hours correlated significantly with length of ICU stay and postoperative blood product administration.
16 However, this study did not report outcome related with LCOS. Another study measured inflammatory mediators
17 (IL-6, IL-8, IL-10, and TNF α) and cardiac markers (N-terminal pro-B-type natriuretic peptide and troponin I) in 46
18 cardiac pediatrics patients¹⁴. Multivariate logistic regression identified pre-operative N-terminal pro-B-type natriuretic
19 peptide □ 470 fmol/ml and post-operative IL-8 at 4 hour □ 128 pg/ml were significantly related with LCOS events.

20 The most recent study published in 2021¹⁵ evaluated inflammatory mediators in 31 patients with congenital
21 heart disease. It showed higher preoperative IL-10 and 24-hour postoperative IL-8 level were associated
22 significantly with LCOS.

23 **Research methodology**

24 **9.1. Study design:** prospective diagnostic study

25 **9.2. Setting of the study/Trial site:** 8-bed pediatric intensive care unit, Songklanagarind Hospital, Hat Yai,
26 Songkhla

27 **9.3. Target population:** Children with cardiac disease in Songklanagarind hospital who undergone open
28 cardiac surgery with cardiopulmonary bypass (age < 18 years old)

29 **9.4. Study population**

30 **9.4.1. Inclusion criteria:**

- 31 - Children aged 0-18 years old with either congenital or acquired cardiac disease
- 32 - Undergone cardiopulmonary bypass for cardiac surgery
- 33 - Be admitted in PICU for post-operative care

34 **9.4.2. Exclusion criteria**

- 35 - Preterm infant (GA < 37 weeks) or weight less than 2 kg

1 - Patient who weaned off cardiopulmonary bypass and required extracorporeal membrane
2 oxygenator (ECMO) before leaving the operating room
3 - Patient who required emergency cardiac operation within 24 hour after hospitalization
4 - Patient who had significant residual left side outflow tract obstruction (e.g., coarctation of
5 aorta, interrupted aortic arch) which defined by difference of SBP between upper and lower
6 extremities more than 10 mmHg
7 - Patient who had already participated in another research project
8 - Patient who does not have both arterial line and central line catheter back from operating room
9 - Parents or legal guardian refuse to inform consent.

10 9.4.3. Withdrawal criteria:

11 - Parents or legal guardian request to withdraw from research

12 9.4.4. Termination criteria: none

13 **9.5. Sample size calculation**

14 For the 1st objective, we apply diagnostic study as follows:

$$n = n_0 / \text{prevalence or incidence of disease}$$

$$n_0 = \frac{(Z_{\alpha/2})^2 P (1-P)}{d^2}$$

15	Where: Sensitivity (p)	= 0.85
16	Precision (d); not more than 10% of p	= 0.09
17	Alpha	= 0.05

18 We applied the sensitivity of lactate > 3 mmol/L for major morbidity, which defined as at least one of
19 complications (i.e., neurological, pulmonary, gastroenteric, and need for extracorporeal membranes oxygenation or
20 ventricular-assist device, or sepsis)¹⁶.

21 Estimated patient (n_0) is 61 cases. Based on 48% of incidence of LCOS-related outcome last year in our
22 study setting, the required total sample size including non-disease and disease participants will be 128 (=61/0.48).

23 Regarding with our sample size calculation for two objectives and an estimate of 20% of unusable data
24 from a sample of 128 participants has been considered. The final sample size is 154 participants for sensitivity of
25 0.85. However, we will collect blood sample for inflammatory markers in 32 patients for preliminary analysis.

26 **9.6. Variables of the study**

27 9.6.1. Dependent variable: poor outcomes indirectly represented from low cardio output syndrome

28 - LCOS-related poor outcome is modified from the study of Drennan SE, et al and Carmona, et al^{14, 15}
29 which consisting of at least two of the following criteria within 48 hour post operatively:

- 1 a. Clinical findings suggestive of LCOS: prolonged capillary refill > 3 s, systolic blood pressure < 5th
2 percentile for age and gender, persistently elevate of LA pressure above 10 mmHg for at least 6 hr
3 , low urine output (< 1mL/kg/hr) for at least 6 hour despite diuretic use
- 4 b. Laboratory findings suggestive of LCOS: persistently elevated lactate (>2 mmol/L), metabolic
5 acidosis with an increase in the base deficit (>4 mmol/L) for at least 6 hr consecutively.
- 6 c. Vasoactive-inotropic score (VIS) \square 20
- 7 d. Any unplanned surgical reinterventions, cardiac arrest, or utilization of extracorporeal membrane
8 oxygenator (ECMO) within 48 hours
- 9 e. Left ventricular fraction less than 50% by echocardiography

10 The LCOS-related outcome will include both anatomical LCOS and physiological LCOS that caused by

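### Section 9.5 limits d to 10% of p (0.085) but calculates with d = 0.09 (10.6% of p), so 61 cases and 128 children do not meet the stated limit

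*Combined protocol and SAP*

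**What the plan says.** Section 9.5 (Sample size calculation) uses the usual formula for estimating one proportion, with a two-sided normal quantile, for the first objective. Its inputs are "Sensitivity (p) = 0.85", "Precision (d); not more than 10% of p" (entered as 0.09) and alpha = 0.05.

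The result is given as "Estimated patient (n_0) is 61 cases". This is divided by the expected share of children with the outcome ("Based on 48% of incidence of LCOS-related outcome last year in our" study setting) to give 128. An allowance for 20% unusable data "from a sample of 128 participants has been considered" then gives a final sample size of 154.

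**The concern.** The precision line holds both a rule and a number, and the number breaks the rule. The rule is relative to p and is an upper limit: 10% of 0.85 is 0.085. The number is 0.09. Rounding 0.085 to two decimals may explain this, although the document does not say so; in any case, an upper limit cannot be met by rounding up.

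Because d is squared in the formula, the difference carries into the number of cases. Section 9.5 is the only precision justification for the primary objective, and sensitivity is one of the accuracy indices that section 9.11 names for it. Someone who takes the 10% rule at face value would expect tighter precision than the sample size is expected to give.

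**Working it through.** **Inputs, all from section 9.5:** p = 0.85; d = 0.09 as entered, or 0.10 × 0.85 = 0.085 as the rule requires; alpha = 0.05 two-sided, so z = 1.96; incidence 48%; 20% allowance.

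**Formulas.** Cases: n0 = z² × p(1 − p) / d², with p(1 − p) = 0.85 × 0.15 = 0.1275. Total: n = n0 / 0.48. Enrolled: n × 1.2. Fractions are rounded up at each step.

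**Both versions of d:**

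| Step | d = 0.09 (entered) | d = 0.085 (10% of p) |
|---|---|---|
| d / p | 10.6% | 10.0% |
| n0 | 60.47 → 61 | 67.79 → 68 |
| n0 / 0.48 | 127.1 → 128 | 141.7 → 142 |
| × 1.2 | 153.6 → 154 | 170.4 → 171 |

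The left column reproduces all three of the plan's figures, so 0.09 is the value that was used. The right column is what the stated rule needs. The differences are 68 − 61 = 7 cases, 142 − 128 = 14 children and 171 − 154 = 17 enrolled. The ratio before rounding is (0.09 / 0.085)² = 1.12.

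**Expected precision.** Half-width = 1.96 × √(0.1275 / cases), against a limit of 0.085:

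| Situation | Cases | Half-width | Share of p |
|---|---|---|---|
| 128 children usable (26 of 154 lost) | 61 | 0.0896 | 10.5% |
| 20% of 154 lost, about 123 usable | 59 | 0.091 | 10.7% |
| 142 children usable | 68 | 0.0849 | 10.0% |
| All 154 usable | 74 | 0.081 | 9.6% |

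Rounding 60.47 up to 61 does not rescue the limit. With 128 usable children the entered d = 0.09 is just met and the 10% rule is not. If the 20% loss applies to the 154 enrolled, 0.09 is narrowly missed as well.

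**Dependence on the incidence.** For an assumed range of 43% to 53% (the documents give only 48% for this setting and outcome), 128 usable children give about 55 to 68 cases and a half-width of 0.094 to 0.085. Within that range the limit is reached only at the top.

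**The case against.** The best defence is that this is a loose label rather than a faulty design. Section 9.5 gives its inputs to two decimals, 0.085 to two decimals is 0.09, and the value used is printed openly, so any reader can reproduce 61, 128 and 154. No analysis in section 9.11 uses the 10% rule. The gap is also inside ordinary planning uncertainty: if the true sensitivity were 0.87, 61 cases would give a half-width of 0.084 against a limit of 0.087. All of this stands and bears on how much the point matters. It does not make 0.09 comply with a limit of 0.085. Reading the rule as ten percentage points would, but the text says 10% of p.

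A second defence is that 154 children are enrolled, not 128. The limit is met at 48% incidence if at least 142 are usable, that is, if no more than 12 of 154 (7.8%) are lost. Several provisions make loss of a whole child less likely: children without both lines are excluded (section 9.4.2), line displacement makes only the later samples missing (section 9.7, item 10), and data collected before withdrawal are kept (section 10.5). Early time points may therefore retain more than 128 children. But the plan's own estimate is 20% unusable data, and at that rate the limit is missed.

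It is also fair to say that the document does not call the 128 usable. That is a reading, based on the 20% being added on top of it.

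**Conclusion.** The point holds and its impact is low. The precision rule and the precision value in section 9.5 disagree, and the sample size was built on the looser of the two. Against the stated rule, the plan is short by 7 cases, or 14 children before the allowance. The expected half-width with 61 cases is 0.0896 instead of at most 0.085. The calculations from d = 0.09 onward are correct on their stated base.

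The shortfall rests on p = 0.85, 48% incidence and loss of about the planned number of whole children. The contradiction between 0.085 and 0.09 rests on no assumption.

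**What to change.** Restate the precision line in section 9.5 as: Precision (d) = 0.09 (10.6% of p). Leave 61, 128 and 154 unchanged, since they follow from 0.09. This costs one line of wording, with no change to enrolment, procedures or analysis. The stated relative precision becomes slightly less favourable, 10.6% instead of 10%.

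If the 10% rule is the one intended, the alternative is d = 0.085 with 68 cases, 142 children and 171 enrolled by the plan's own method, at a cost of 17 more children.

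As an optional clarification, not an error, section 9.5 could note that the 26 added children are 20% of 128, which is about 17% of the 154 enrolled (26 / 154).

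### The 20% allowance in section 9.5 is applied as 128 × 1.2 = 154, which covers a loss of 16.9% of enrolled children; at a 20% loss among those enrolled, about 123 remain instead of 128

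*Combined protocol and SAP*

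**What the plan says.** Section 9.5 sizes the study on the precision of a sensitivity estimate. The inputs are "Sensitivity (p) = 0.85", "Precision (d); not more than 10% of p = 0.09" and alpha 0.05. The result is "Estimated patient (n_0) is 61 cases". The section then scales up to all children, cases and non-cases together: "Based on 48% of incidence of LCOS-related outcome last year in our" study setting, "the required total sample size including non-disease and disease participants will be 128 (=61/0.48").

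The allowance follows in one sentence and the total in the next: "Regarding with our sample size calculation for two objectives and an estimate of 20% of unusable data" "from a sample of 128 participants has been considered. The final sample size is 154 participants for sensitivity of" 0.85. The inflation formula is not written out. No other section gives a different total or a different loss rate.

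**The concern.** The section treats 128 as the number required, so it is the number that should still be available once unusable records are set aside. Unusable records arise among the children enrolled. A loss rate stated for enrolled children is therefore covered by dividing by one minus the rate, not by multiplying by one plus the rate. Multiplying always gives a smaller total, and the total then misses its target at the very loss rate it is meant to absorb.

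What is at stake is whether the headline enrolment figure, which supports the primary objective, delivers the case count from which it was built. Some loss is foreseeable here. Section 9.7 accepts paired gases only when drawn within 5 minutes of each other (item 5) and records data after catheter displacement as missing (item 10).

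**Working it through.** Inputs, all from section 9.5: sensitivity P = 0.85, half-width d = 0.09, alpha = 0.05 (z = 1.96), incidence 0.48, allowance 20%. The value d = 0.09 is accepted as it stands.

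**Reproducing the plan's figures**

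1. Cases: n0 = z² P(1 − P)/d² = 1.96² × 0.85 × 0.15/0.09² = 60.47, rounded up to 61. Matches.
2. Children: 61/0.48 = 127.08, rounded up to 128. Matches.
3. Allowance by multiplication: 128 × 1.2 = 153.6, rounded up to 154. Matches.
4. Allowance by division: 128/0.8 = 160. Without the intermediate rounding, 127.08/0.8 = 158.9, so 159. Neither gives 154.

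**What each total leaves if 20% of those enrolled are unusable**

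| Enrolled | Usable (× 0.8) | Expected cases (× 0.48) | Half-width, 1.96 × √(0.1275/cases) |
|---|---|---|---|
| 154 | 123.2 | 59.1 | 0.0910 |
| 160 | 128.0 | 61.4 | 0.0893 |

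Here 0.1275 = 0.85 × 0.15. With exactly 61 cases the half-width is 0.0896.

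**The loss that 154 does cover**

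154 − 128 = 26, and 26/154 = 16.9%. Up to that share of enrolled children can be lost with 128 still usable.

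**Size of the shortfall at 20%**

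- Usable children: 128 − 123.2 = 4.8.
- Expected cases: 61 − 59.1 = 1.9 against the rounded target, or 60.47 − 59.14 = 1.3 against the unrounded one.
- Half-width: 0.091 against the planned 0.09.

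**The case against.** The strongest defence is that the section names its own base. Read literally, the 20% is taken of the 128: 25.6, rounded up to 26, and 128 + 26 = 154. On that reading the sum is correct and only the base of the percentage is unclear. This explains how 154 arose. It does not make 154 sufficient for a 20% loss among enrolled children, because 26 of 154 is 16.9%, and the section does not tell the reader so.

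Other parts of the defence stand and limit the point:

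- A reader might infer that 154 cannot yield 128 usable children. It can, whenever the loss is 16.9% or less, and the 20% is itself only an estimate with no source given.
- A reader might infer that the stated precision is lost. The plan gives d to two decimals, and 0.091 rounds to 0.09.
- The figure of 123 assumes that an affected child contributes nothing. Section 9.7 item 10 makes only the data after catheter displacement missing, and section 10.5 keeps data collected before withdrawal. At a given time point 123 is therefore a pessimistic count.
- The gap is small beside the uncertainty in the inputs. The number of cases among 123 children has a binomial standard deviation of √(123 × 0.48 × 0.52) ≈ 5.5. An incidence of 61/123 = 49.6% instead of 48% would close the gap, and the 48% comes from one year at one site.

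**Conclusion.** The point holds in a limited form. The total of 154 comes from multiplying by 1.2 and does not protect the required 128 children and 61 cases against a 20% loss among those enrolled. It protects them against a loss of up to 16.9%. At 20% the expected shortfall is about 5 usable children and 1 to 2 cases, with a half-width of about 0.091.

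This rests on three assumptions: the 20% refers to enrolled children, a lost child is lost entirely, and incidence is 48%. The case counts are expectations, and the observed number will vary.

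The documents do not support a conclusion that the study is materially too small, that its precision target fails at the accuracy to which it is stated, or that 160 children must be enrolled. What needs correcting is a headline figure whose description does not match the loss it covers.

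**What to change.** Keep 154 and restate the last line of section 9.5 so that it says three things:

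- the allowance is 20% of 128, that is 26 children, equal to 16.9% of the 154 enrolled;
- if 20% of those enrolled prove unusable, about 123 children and 59 cases are expected, with a half-width of ±0.091;
- 160 (= 128/0.8) is the total that would fully cover a 20% loss, given for reference.

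The cost is a short rewording of one line, with no extra children and no change to the analysis. If d or the incidence in 9.5 is revised for another reason, these figures should be recalculated from the new inputs.

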11 CPB

[figure not shown]
- 12 - Vasoactive-Inotropic Score (VIS) based on Belletti A, et al¹⁷ which is summation of dopamine dose
13 (mcg/kg/min) + dobutamine dose (mcg/kg/min) + 100 x epinephrine dose (mcg/kg/min) + 10 x milrinone
14 dose (mcg/kg/min) + 100 x norepinephrine dose (mcg/kg/min) + 10000 x vasopressin dose (U/kg/min)
15 + 50 x levosimendan dose (mcg/kg/min) + 20 x methylene blue dose (mg/kg/h) + 10 x phephylephrine
16 dose (mcg/kg/min) + 10 x terlipressin dose (mcg/min) + 0.25 x angiotensin II dose (ng/kg/min)
- 17 - Acute kidney injury (AKI) based on KDIGO guideline 2012¹⁸ defined AKI as any of following: increased
18 in SCr by \square 0.3 mg/dL within 48 hours, or increased in SCr to \square 1.5 times baseline, which is known
19 or presumed to have occurred within the prior 7 days, or urine volume < 0.5 mL/kg/h for 6 hours
- 20 - 28 ventilator free day (VFDs) and 28 ICU free day (IFDs): the number of days those patients were alive
21 and free from invasive ventilator or ICU stay within 28 days by counting the day of first operative night
22 as the first day. VFDs and IFDs will be counted as zero in non-survivor patients.

23 9.6.2. Independent variables: AVCO₂, ScvO₂, lactate, inflammatory markers at 0, 6, 12, and 24 hour after
24 operation with additional inflammatory markers at pre-operative stage

25 9.6.3. Potential confounder variables: age, gender, risk stratification for cardiac surgery (RACHS score),
26 nutritional status, duration of bypass time or aortic clamp time

27 9.6.4. Methods to minimize bias during study: we will blind the result of inflammatory markers to attendant
28 physician by sending blood sample to research lab which will not be reported in HIS system. Blood
29 sample collection and processing time will be fixed to ensure laboratory quality of the specimen and
30 its interpretation.

31 32 **9.7. Study procedure(s)/stage(s)**

1. Researcher will introduce research project verbally to cardiac pediatrics patient or their legal guardians at cardiac outpatient clinic when he/ she are scheduled to have cardiopulmonary bypass surgery at Songklanagarind Hospital. Researcher will later request patient or legal guardians to sign the informed consent when he/she is admitted in hospital 24 hours in advance.

2. If patient has already been admitted in hospital for any reason and have schedule for surgery, researcher will inform patient or legal guardians 48 hours in advance.

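### A child can be counted as a case on criteria b and c alone, and one beta-agonist infusion may feed both, so the AVCO2-versus-lactate comparison may be tilted toward lactate

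*Combined protocol and SAP*

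**What the plan says.** Section 9.6.1 defines the LCOS-related poor outcome as one "which consisting of at least two of the following criteria within 48 hour post operatively". The five criteria are clinical findings (a), laboratory findings (b), the vasoactive-inotropic score, VIS (c), major events (d) and reduced left ventricular function on echocardiography (e). None is mandatory and no pair is ruled out.

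Criterion b begins "Laboratory findings suggestive of LCOS: persistently elevated lactate (>2 mmol/L), metabolic" and continues "acidosis with an increase in the base deficit (>4 mmol/L) for at least 6 hr consecutively". Only a comma separates lactate from acidosis. The text does not say whether either one is enough or both are needed.

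Criterion c is a VIS threshold of 20 (read here as reaching 20), with no duration, time point or indication. The formula given later in 9.6.1 adds drug doses and nothing else, for example "100 x epinephrine dose (mcg/kg/min) + 10 x milrinone" dose.

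Section 6 says of lactate, ScvO2 and AVO2: "However, these parameters can be influenced by multiple factors unrelated to LCOS". On lactate it continues: "Hyperlactatemia in cardiac surgery could be elevated due to post-operative stress response, use of beta"-adrenergic agonists, and other causes.

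Section 9.11 compares AVCO2 with the traditional surrogates on sensitivity, specificity, predictive values and ROC area. It plans one sensitivity analysis (physiological LCOS) and one subgroup analysis (univentricular versus biventricular repair).

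**The concern.** A two-of-five rule is meant to make one criterion corroborate another. That works only if the two criteria are separate pieces of evidence. Criterion c records treatment given. If the same treatment can also raise the lactate in b, the pair b + c may be one observation counted twice.

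The primary objective is a head-to-head comparison of AVCO2 with lactate, ScvO2 and AVO2. A child who is a case because of drug-raised lactate plus VIS will tend to be flagged by lactate, since raised lactate is how that child became a case. AVCO2 is described in Section 6 as a measure of how well the circulation clears CO2, so it may be unremarkable in the same child. The labelling error would then fall unequally on the two markers and could affect their ranking, rather than only adding noise.

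**Working it through.** **1. The plan's own figures (Section 9.5).** Inputs: P = 0.85, d = 0.09, two-sided alpha 0.05, incidence 48%, 20% unusable data.
- n0 = 1.96² × 0.85 × 0.15 / 0.09² = 60.47, rounded up to 61.
- 61 / 0.48 = 127.1, rounded up to 128.
- 128 × 1.2 = 153.6, rounded up to 154.

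All three reproduce. Expected cases among 128 usable children: 0.48 × 128 = 61.4. The 0.85 is a published sensitivity of lactate above 3 mmol/L for major morbidity. It is not a figure for AVCO2.

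**2. Which combinations qualify.** Five criteria give 10 pairs, and 26 combinations of two or more. Exactly one of the 26 contains none of a, d or e: b and c together with nothing else. The b + c-only children are therefore a single, countable group. A rule that also requires a, d or e differs from the primary rule in these children only.

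**3. Can one exposure feed both criteria?**
- *Criterion c:* yes, by construction. From the formula, a single agent reaches 20 at epinephrine 20/100 = 0.2 mcg/kg/min, or dobutamine 20/1 = 20 mcg/kg/min. This is arithmetic on the protocol's weights and says nothing about appropriate dosing.
- *Criterion b, if lactate alone suffices:* possible on the protocol's own statement in Section 6.
- *Criterion b, if lactate and base deficit are both needed:* not supported. Section 6 links beta-agonists to lactate, and nothing in the documents links them to a base deficit above 4 mmol/L for 6 hours.

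The list style of criterion a suggests that either item may suffice, but the text does not settle it.

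**4. Effect on the comparison.** Let f be the share of labelled cases that are b + c only, and s the sensitivity of both markers in the other cases (taken as equal). Let r and q be the fractions of b + c-only cases flagged by lactate and by AVCO2.
- Apparent sensitivity of lactate: (1 − f)s + f·r
- Apparent sensitivity of AVCO2: (1 − f)s + f·q
- Spurious gap in favour of lactate: f(r − q)

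The documents give none of f, r or q. With assumed r = 1 and q = 0.40, the gap is 0.10 × 0.60 = 0.06 at f = 10% and 0.30 × 0.60 = 0.18 at f = 30%. If r = q, the gap is zero. Nor is r = 1 assured: index lactate is read at 0, 6, 12 and 24 hours and Section 9.11 sets no cut-off, whereas criterion b uses 2 mmol/L over 48 hours. The range therefore starts at nothing, and the documents do not narrow it.

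**5. Would a planned analysis show it?** The 9.11 analyses split children by type of LCOS and by type of repair, not by which criteria were met. The text gives no operational definition of physiological LCOS, and a figure next to the sentence that introduces it is not available here. Some overlap with the b + c-only group cannot be excluded.

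**The case against.** The best defence is that b + c is what treated low output looks like. The protocol itself lists b as suggestive of LCOS, and a child on enough support to reach a VIS of 20 may have acceptable pressure and perfusion because of that support. This stands: the documents cannot separate treated low output from a false label. A reader might infer that b + c-only children show no sign of low output, but the text supports only that none of a, d or e need be met.

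A second defence is that a stricter rule has faults of its own. Section 6 notes the absence of consensus criteria, and the outcome is adapted from two published studies. Requiring a, d or e would turn supported low-output children into non-cases, where a high AVCO2 counts as a false positive. Nor are a and d perfect anchors: capillary refill and systolic pressure carry no stated duration, and unplanned reintervention is not specific to low output. This also stands, and it is why the primary definition should not be replaced.

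A third is that the mechanism depends on one reading of b. That is correct, and the conclusion is conditional on it. None of these points argues against counting the group and testing whether the result depends on it.

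**Conclusion.** The structural point holds: b + c alone makes a case. If lactate alone meets b, the two criteria are not independent evidence, and the primary comparison may be tilted toward lactate. No planned analysis is defined by which criteria were met. The size is unknown, and the direction rests on lactate flagging these children more often than AVCO2 does.

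Three stronger readings go beyond the documents:
- A reader might infer that ordinary support carried over from the operating room is enough to meet c. No usual regimen or VIS distribution is given, so this cannot be shown.
- A reader might infer an expected loss of AVCO2 sensitivity of 4.5 to 13.5 points, from 0.85 × 0.90 + 0.40 × 0.10 = 0.805 and 0.85 × 0.70 + 0.40 × 0.30 = 0.715, against a planned precision of 9 points. The 10–30% share and the 0.40 are assumptions, and the 0.85 belongs to lactate. It is an illustration only.
- A reader might infer that VIS must be sustained for 6 hours to count. The only basis would be symmetry with criterion b.

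Lactate serving as both index test and outcome component is a related but separate issue. It remains in every case that meets b.

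**What to change.** Keep the primary definition and its thresholds. Then:
1. In 9.6.1, state whether criterion b needs raised lactate, base deficit, or both.
2. Record which criteria each case met, and tabulate the number qualifying on b + c only.
3. In 9.11, prespecify a sensitivity analysis of the primary AVCO2-versus-surrogate comparison in which a case must meet at least two criteria, including at least one of a, d or e. Run it with b + c-only children excluded as indeterminate, and again with them counted as non-cases. Show both beside the primary result.

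Both runs are needed. Exclusion avoids labelling these children either way. Counting them as non-cases tests the opposite label, but it may misclassify treated low output and turns their raised lactate into false positives.

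Section 9.7 already collects haemodynamics, interventions and echocardiography, so the cost is wording and one rescoring, with no new sampling and no change to care. The price is fewer cases and wider intervals in the added analysis. With 128 usable children and sensitivity 0.85, cases are 61.4 × (1 − f) and the half-width is 1.96 × √(0.85 × 0.15 / cases):

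| Assumed b + c-only share f | Cases left | Half-width |
|---|---|---|
| 5% | 58.4 | 0.092 |
| 10% | 55.3 | 0.094 |
| 20% | 49.2 | 0.100 |
| 30% | 43.0 | 0.107 |

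The planned half-width is 0.09, so the loss is modest unless the group is large, in which case the trial needs to know that.
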